1.3. Previous Clinical Study Experience with ATI-501

Eight Phase 1 clinical studies were conducted with ATI-501 oral doses ranging from single ascending doses of ATI-501 of 50 mg to 500 mg and multiple ascending doses of 200, 400 mg, 600 mg and 800 mg BID for 14 days. A total of 186 healthy volunteers were exposed to oral doses of ATI-501. Single and twice-daily doses of ATI-501 were well-tolerated. There were no SAEs reported in the eight completed clinical studies.

In study ATI-50001-AUAT-106, the multiple ascending dose study, 54 subjects received doses up to 800 mg BID for 14 days. The most frequently reported treatment related adverse events (TRAE) reported in more than 1 subject were: headache (14.8%), abdominal discomfort (9.3%), decreased appetite (9.3%), dizziness (7.4%), somnolence (7.4%), diarrhea (5.6%), dry skin (5.6%), nausea (5.6%), constipation (3.7%), dyspepsia (3.7%), feeling hot (3.7%) and paresthesia (3.7%).

No clinically significant laboratory abnormalities were observed. There were no clinically significant findings from 12-lead ECGs. One subject experienced a transient elevation in blood

Date: 09NOV2018, Version 1.0 Page 18 of 80 CONFIDENTAL

pressure (pre-dose 126/85mmHg, 4 hours post dose 142/104 mm/Hg) which was assessed as clinically significant by the investigator. The subjects blood pressure returned to within normal limits at all other assessed timepoints throughout the study. There were no other clinically significant findings from vital signs assessments.

In study, ATI-50001-AUAT-106, ATI-501 was not detected in plasma and there was a dose-related increase in plasma of the active metabolite ATI-502. Systemic levels of ATI-502, following oral doses of ATI-501 in healthy volunteers transiently reduced pSTAT5 activity in ex vivo IL-2 stimulated lymphocytes, indicating inhibition of the JAK signaling pathway. Upon multiple dosing, pSTAT5 activity showed a more sustained inhibition during the dosing period.

Non-clinical studies conducted with topical administration of ATI-502 support the topical administration of ATI-502 (ATI-502 Investigator Brochure).

1.4. Clinical Study Experience with ATI-502 Topical Solution

Seven Phase 2 clinical studies are ongoing with ATI-502 Topical Solution 0.46%, 0.12% or placebo solution. ATI-50002-AA-201 is a randomized, double-blind vehicle-controlled study in subjects with stable patchy alopecia areata. ATI-50002-AA-202 is a randomized double-blind, vehicle-controlled study in subjects with alopecia universalis or alopecia totalis. ATI-50002-AUATB-201 is an open-label pilot study of the safety, tolerability and efficacy of ATI-50002 topical solution administered twice-daily in adult subjects with eyebrow loss due to alopecia areata, alopecia universalis or alopecia totalis. ATI-50002-AAB-201 is an open-label pilot study of the safety, tolerability and efficacy of ATI-50002 topical solution administered twice-daily in adult subjects with eyebrow loss due to alopecia areata, alopecia universalis or alopecia totalis. ATI-50002-VITI-201 is an open-label pilot study of the safety, tolerability and efficacy of ATI-50002 Topical Solution Administered Twice-Daily in adult subjects with non-segmental facial vitiligo. ATI-50002-AGA-201 is an open-label safety, tolerability, and efficacy study in male and female subjects with androgenetic alopecia treated with ATI-50002 Topical Solution. ATI-502-AD-201 is a phase 2a safety study of ATI-502 Topical Solution in subjects with moderate to severe atopic dermatitis.

As of July 2018, 141 subjects have applied ATI-502 Topical Solution 0.46%, 0.12% or Placebo solution bid for up to 6 months or longer. Two unrelated serious adverse events were reported in one subject each: laceration and depression. The studies are ongoing, adverse events reported to date have been primarily transient and mild in severity. Local application site reactions occurring in one subject in the individual studies have included administration site pain, application site pruritus, application site erythema, application site swelling, erythema, pain of skin, pityriasis rosea, rash, acne, alopecia, and in two subjects; pruritus.

1.5. Study Rationale

Protocol: ATI-502-AA-203

Several published case reports have demonstrated the potential for JAK1/3 inhibitors to induce hair growth in patients with AA (Kim 2017, Craiglow 2014 and 2017, Gupta 2016, Scheinberg 2016). These AA case reports have shown promising results with oral tofacitinib and ruxolitinib treatment. However, so far, JAK inhibitors have not been shown to provide long-term efficacy after ending oral treatment. Hair shedding and substantial hair loss have been reported soon after cessation of treatment with oral JAK inhibitors (Mackay-Wiggan 2016).

Date: 09NOV2018, Version 1.0 Page 19 of 80 CONFIDENTAL

Among patients with AA, patients with higher disease burdens are unlikely to have satisfactory outcomes with current therapies. Aclaris Therapeutics, Inc. is developing ATI-502 as a treatment for stable patchy AA, AU or AT. ATI-501 is an oral prodrug that is rapidly converted presystemically to ATI-502, a potent highly selective inhibitor of Janus kinase 1 (JAK1) and Janus kinase 3 (JAK3). This study will evaluate the safety and efficacy of ATI-502 Topical Solution in the treatment of subjects with AA, AU or AT. In addition, the study will assess whether topical treatment with ATI-502 Topical Solution will maintain hair regrowth in subjects who completed 24 weeks of treatment with ATI-501 Oral Suspension or Placebo Suspension in study ATI-501-AUAT-201.

1.6. Study ATI-501-AUAT-201

Protocol: ATI-502-AA-203

Study ATI-501-AUAT-201 is an ongoing Phase 2, multicenter, randomized study designed to evaluate the safety, tolerability and efficacy of ATI-501 for the treatment of AA, AU, or AT in adult subjects. During the screening period, subjects were assessed for eligibility into the study. Eligible subjects were male and non-pregnant, non-nursing females ≥ 18 years of age, who were in good general health and free of any known disease or physical condition which might impair evaluation of the subject. Subjects were excluded from enrollment if they had a history of or current systemic or cutaneous malignancy (except for adequately treated and well healed, and completely cleared non-melanoma skin cancers), had evidence of active or latent bacterial or viral infections (including herpes zoster or disseminated herpes zoster or disseminated herpes simplex), a history of a serious local infection within 3 months prior to baseline or were positive for active tuberculosis, HIV, Hepatitis B or C infection. Subjects with serologic evidence of Hepatitis B vaccination were allowed to participate.

Enrolled subjects were required to have a clinical diagnosis of stable AA, AU, or AT with 30% to 100% total scalp hair loss (based on SALT score at baseline) for a duration of at least 6 months up to and including 12 years. Subjects who met the entry criteria were randomized to take ATI-501 Oral Suspension, 400 mg, 600 mg, 800 mg or placebo suspension twice-daily for 24 weeks. Assessment of response to treatment is being performed at Week 4, Week 8, Week 12, Week 16, Week 20, Week 24, and post-treatment Week 28.

Subjects who complete ATI-501-AUAT-201 study visits up to and including Week 24 (Visit 9) are eligible to enter this study. At Visit 9 (in study ATI-501-AUAT-201), subjects who agree to participate in study ATI-502-AA-203, must sign consent prior to first application of topical study medication. The assessments completed at Visit 9 (study ATI-501-AUAT-201) will be entered into the source documentation for Visit 1 in study ATI-502-AA-203. Subjects who meet the ATI-502-AA-203 entry criteria will apply ATI-502 Topical Solution, 0.46% BID for 24 weeks followed by a 4-week post-treatment follow up visit.

Date: 09NOV2018, Version 1.0 Page 20 of 80 CONFIDENTAL

2. TRIAL OBJECTIVES AND ENDPOINTS

2.1. Objectives

Protocol: ATI-502-AA-203

The primary objective is to assess the safety, tolerability, and efficacy of ATI-502 Topical Solution in subjects with AA, AU or AT following 24 weeks of treatment with ATI-501 Oral Suspension or Placebo Suspension in Study ATI-501-AUAT-201.

An additional objective is to assess the ability of ATI-502 Topical Solution to maintain or improve hair regrowth in subjects with AA, AU or AT following 24 weeks of treatment with ATI-501 Oral Suspension or Placebo Suspension Study ATI-501-AUAT-201.

2.2. Efficacy Endpoints

The efficacy endpoints will evaluate the assessment (specified in Section 2.2.1 and Section 2.2.2) from the Baseline visit from both ATI-501-AUAT-201 and ATI-502-AA-203 compared to the applicable post-baseline visits.

2.2.1. Primary Efficacy Endpoint

The primary efficacy endpoint will be the mean relative percent change from the original baseline visit in study ATI-501-AUAT-201 in the SALT score at Visit 6 (Week 24 on study ATI-502-AA-203). This represents the percentage of hair regrowth. It will be calculated as the mean of the changes from baseline SALT score to the SALT score at Visit 6 (Week 24 on study ATI-502-AA-203), divided by baseline SALT score and expressed as a percentage.

2.2.2. Secondary Efficacy Endpoints:

- Proportion of subjects achieving a SALT 50, SALT 75 (defined as $a \ge 50\%$, $\ge 75\%$ improvement from baseline in SALT) by visit.
- Durability of response: Proportion of subjects achieving a SALT 50 or SALT 75 at Week 24 (study ATI-501-AUAT-201) and maintaining response at post-baseline visits in ATI-502-AA-203.
- Mean Relative Percent Change from Baseline (from the current study ATI-502-AA-203) in Severity of Alopecia Tool (SALT) by visit.
- Mean Relative Percent Change from Baseline in Alopecia Density and Extent Score (ALODEX) score by visit.
- Mean Change from Baseline in SALT and ALODEX score by visit.
- Change from Baseline in the Alopecia Scalp Appearance Assessment (ASAA) (Patient-reported outcome [PRO]) by visit.
- Change from Baseline in the Alopecia Scalp Appearance Assessment (ASAA) (Clinician-reported outcome [ClinRO]) by visit.
- Change from Baseline in the Physician Global Impression of Severity (PhGIS) by visit.
- Change from Baseline in Alopecia Facial Hair Appearance Assessment (AFHA) (Clinician and Subject) by visit.
- Change from Baseline in the Subject Global Impression of Severity (SGIS) by visit.
- Change from Baseline in the subject reported Alopecia Impact Assessment (AIA) by visit.

Date: 09NOV2018, Version 1.0 Page 21 of 80 CONFIDENTAL

Protocol: ATI-502-AA-203

- Subject Global Impression of Treatment Satisfaction (SGITS) by visit.
- Change from Baseline in the Subject Global Satisfaction with Hair Quality (SGSHQ) by visit.
- Global Impression of Change (Clinician and Subject) at Week 24 of ATI-502-AA-203.

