- Hair quality assessment including normalization of exclamation point hairs and hair shedding will be described.
- Vellus and Indeterminate scalp hair will be described.
- Non-scalp hair assessments (body and nasal hair) will be described.

Statistical Methods:

Sample Size/ Power Calculations

The planned sample size 80 enrolled is based on an estimated completion rate from study ATI-501-AUAT-201.

Statistical Methods

Subject demographic and baseline characteristics, including medical and alopecia history, prior medications and therapies and physical examination findings will be summarized using descriptive statistics.

Summary descriptive statistics (N, mean, median, SD) by visit will be provided for all safety and efficacy parameters. The Intent to Treat population will be used for all efficacy assessments and the Safety population will be used for all safety assessments. No data imputation will be used.

No inferential analyses are planned. For all efficacy evaluations described below, summary statistics will be provided for all treated subjects pooled, and also for each of two sub-groups of subjects based on the treatment they previously received in study ATI-501-AUAT-201.

Primary Efficacy Analyses

For the primary endpoint, the primary efficacy variable will be the mean relative percent change from the original baseline visit in study ATI-501-AUAT-201 in the SALT score to Visit 6 (Week 24). This represents the percentage of hair regrowth. It will be calculated as the mean of the changes from baseline SALT score to the SALT score at Visit 6 (Week 24), divided by baseline SALT score and expressed as a percentage.

Date: 09NOV2018, Version 1.0 Page 7 of 80 CONFIDENTAL

Secondary Efficacy Analyses

Protocol: ATI-502-AA-203

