The secondary efficacy endpoints will be calculated using both the current study baseline scores and the baseline scores from study ATI-501-AUAT-201. These endpoints will be evaluated at each visit and will include: the mean relative percent change from baseline in the ALODEX score (percent regrowth); the mean change from baseline in SALT and the mean change from baseline in ALODEX, the proportion of subjects achieving a \geq 50% and \geq 75% hair regrowth compared with baseline; change from baseline in the ASAA (Clinician and Subject), PhGIS, AFHA, SGIS, AIA, and treatment satisfaction questionnaires. The mean relative percent change in ALODEX score analysis will use the same methodology as specified for the primary efficacy analysis. Other parameters will be summarized as detailed in the statistical analysis plan.

Safety Data

Safety analyses will include descriptive statistics calculated on the safety parameters using the safety population. The proportion of subjects with treatment-emergent adverse events will be tabulated and presented by Medical Dictionary for Regulatory Activities (MedDRA) System Organ Class. Vital signs and clinically significant abnormal laboratory results will also be tabulated and presented.

Data from enrolled subjects will be presented and summarized. Safety summaries will include listings by study medication of adverse events incidences within each MedDRA System Organ Class, and changes from pre-dose values in vital signs. Adverse event summaries will be presented showing the proportion of subjects experiencing adverse events, both overall and by MedDRA System Organ Class.

Date: 09NOV2018, Version 1.0 Page 8 of 80 CONFIDENTAL

TABLE OF CONTENTS, LIST OF TABLES, AND LIST OF FIGURES

INVEST	GIGATOR'S AGREEMENT	3
SYNOPS	SIS	4
TABLE	OF CONTENTS, LIST OF TABLES, AND LIST OF FIGURES	9
LIST OF	TABLES	13
LIST OF	F ABBREVIATIONS AND DEFINITIONS OF TERMS	14
1.	INTRODUCTION	16
1.1.	Overview of Alopecia Areata	16
1.2.	Immunopathology & Pathophysiology of AA	17
1.3.	Previous Clinical Study Experience with ATI-501	18
1.4.	Clinical Study Experience with ATI-502 Topical Solution	19
1.5.	Study Rationale	19
1.6.	Study ATI-501-AUAT-201	20
2.	TRIAL OBJECTIVES AND ENDPOINTS	21
2.1.	Objectives	21
2.2.	Efficacy Endpoints	21
2.2.1.	Primary Efficacy Endpoint	21
2.2.2.	Secondary Efficacy Endpoints:	21
2.3.	Safety Endpoints	22
2.4.	Other Assessments	22
3.	INVESTIGATIONAL PLAN	23
3.1.	Overall Study Design.	23
3.2.	Number of Subjects	23

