9.4. Efficacy Analyses

Hair regrowth is determined based on both percent scalp hair regrowth (Baseline SALT – Follow-up SALT/Baseline SALT) and change in absolute percent scalp hair loss from baseline (Baseline SALT – Follow-up SALT). A responder is a subject who achieves a SALT50 or SALT75 defined as $\geq 50\%$, $\geq 75\%$ improvement in SALT score from baseline values in the ATI-501-AUAT-201 study. Durability of response will be assessed in subjects who achieved a SALT50 or SALT75 in study ATI-501-AUAT-201. Results will be summarized using descriptive statistics.

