9.4.1. Primary Efficacy Analyses

For the primary endpoint, the primary efficacy variable will be the mean relative percent change from the original baseline visit in study ATI-501-AUAT-201 in the SALT score at Visit 6 (Week 24 on study ATI-502-AA-203). This represents the percentage of hair regrowth. It will be calculated as the mean of the changes from baseline SALT score to the SALT score at each visit, divided by baseline SALT score and expressed as a percentage.

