9.4.2. Secondary Efficacy Analyses

The secondary efficacy endpoints will be calculated using both the current study baseline scores and the baseline scores from study ATI-501-AUAT-201. These endpoints will be evaluated at each visit and will include: the mean relative percent change from baseline in the ALODEX score (percent regrowth); the mean change from baseline in SALT and the mean change from baseline in ALODEX, the proportion of subjects achieving a \geq 50% hair regrowth compared with baseline; change from baseline in the AAA (Clinician and Subject), PhGIS, AFHA, SGIS, AIA, and treatment satisfaction questionnaires. The mean relative percent change in ALODEX

Date: 09NOV2018, Version 1.0 Page 54 of 80 CONFIDENTAL

score analysis will use the same methodology as specified for the primary efficacy analysis.

Other parameters will be summarized as detailed in the statistical analysis plan.

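### Percent change from the Visit 1 score is undefined for subjects who enter at SALT 0 and lopsided for those who enter near it; absolute change, already planned, should summarise the topical period

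*Combined protocol and SAP*

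**What the plan says.** Section 2.2.2 names the endpoint "Mean Relative Percent Change from Baseline (from the current study ATI-502-AA-203) in Severity of Alopecia Tool (SALT) by visit". Section 2.2 says that the efficacy endpoints evaluate each assessment "from the Baseline visit from both ATI-501-AUAT-201 and ATI-502-AA-203 compared to the applicable post-baseline visits". Section 9.4.2 repeats this: "The secondary efficacy endpoints will be calculated using both the current study baseline scores and the baseline scores from study ATI-501-AUAT-201". Percent change in ALODEX stands in the list that this sentence governs, both there and in the synopsis, which adds: "The mean relative percent change in ALODEX score analysis will use the same methodology as specified for the primary efficacy analysis".

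On the formula, Section 9.4 begins "Hair regrowth is determined based on both percent scalp hair regrowth" and gives, in brackets, the fall in SALT over baseline SALT. It then gives absolute change as a second measure. Section 9.4.1 describes the percent change as "calculated as the mean of the changes from baseline SALT score to the SALT score at each visit, divided by baseline SALT score". The synopsis states: "Summary descriptive statistics (N, mean, median, SD) by visit will be provided for all safety and efficacy parameters".

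On the possible size of the denominator:

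- Section 1.6: parent-study entry required a baseline SALT of 30 to 100.
- Sections 4.1 and 4.2: entry to this study has no SALT or ALODEX limit. Inclusion criterion 5 admits a subject whom the investigator judges able either to regrow hair or to hold earlier regrowth.
- Table 3, footnote 1: Visit 9 scores of the parent study become the Visit 1 scores. They are repeated only if entry falls more than 14 days after Visit 9.
- Section 9.2: observed cases, no imputation.

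On responders, Section 9.4 defines SALT50 and SALT75 by "improvement in SALT score from baseline values in the ATI-501-AUAT-201 study".

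**The concern.** A percent change needs a denominator that stays clear of zero. The parent-study baseline has that protection for SALT; the Visit 1 score does not, because it is measured after 24 weeks of oral drug or placebo. The better a subject did on oral treatment, the smaller the denominator in this study.

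Those subjects are the ones the additional objective in Section 2.1 is about: people with regrowth that topical treatment may or may not hold. Section 1.5 itself reports substantial hair loss soon after oral JAK inhibitors are stopped, so loss from a low Visit 1 score is foreseeable. A complete regrower has no value in the Visit 1-based percent table, even after a full relapse. A near-complete regrower who relapses can dominate the mean. A table meant to describe the topical period on its own could then omit or distort the subjects it most needs to show.

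**Working it through.** The plan gives no figure to reproduce here: no power, effect size, SD or Visit 1 distribution. The check uses the Section 9.4 formula, read as regrowth % = 100 × (B − F)/B, where B is the baseline score and F the follow-up score.

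**What follows from the plan's own definitions**

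1. Maximum: F = 0 gives 100 × B/B = +100% for any B above 0.
2. B = 0: division by zero, so no value. No zero-denominator rule appears in the text. With observed cases and no imputation, such a subject would by default drop out of the table.
3. A SALT75 responder at Visit 9 has at most 25% of the parent baseline P left. Carried over as Visit 1, that is at most 0.25 × 30 = 7.5 when P = 30 and at most 0.25 × 100 = 25 when P = 100.
4. Relapse to P then gives 100 × (7.5 − 30)/7.5 = −300%, or 100 × (25 − 100)/25 = −300%. A lower Visit 1 score gives a worse figure: 100 × (1 − 30)/1 = −2900%.

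**Effect on a mean of 80 (illustration; the scores are assumed)**

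Let 79 subjects go from 50 to 40 (+20% each; summed change 790, summed baseline 3950) and let one subject relapse.

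| Relapsing subject | Mean of per-subject ratios | Median | Mean change / mean baseline | Mean absolute change |
|---|---|---|---|---|
| 7.5 to 30 | (1580 − 300)/80 = +16.0% | +20% | (790 − 22.5)/(3950 + 7.5) = +19.4% | 767.5/80 = +9.6 points |
| 1 to 30 | (1580 − 2900)/80 = −16.5% | +20% | (790 − 29)/(3950 + 1) = +19.3% | 761/80 = +9.5 points |

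The distortion is modest in the first row and reverses the sign in the second. Median and absolute change barely move.

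**Effect of zeros (illustration; assumed)**

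Let 75 subjects go from 60 to 48 and five go from 0 to 30. The percent table shows +20% on 75 subjects and contains none of the five relapses. Mean absolute change is 12.0 points on those 75, but (75 × 12 − 5 × 30)/80 = 9.4 points on all 80.

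**An alternative SALT scale, (Visit 1 − visit)/parent baseline**

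With P = 30 the relapses become 100 × (7.5 − 30)/30 = −75% and 100 × (1 − 30)/30 = −96.7%. The scale is always defined, but it is not capped at +100%: P = 30, Visit 1 = 100, follow-up = 0 gives 100 × 100/30 = +333%.

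**Responder label**

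Parent 60, Visit 1 80, Week 24 40 is 100 × 40/80 = 50% improvement from Visit 1, but 100 × 20/60 = 33.3% from the parent baseline. This subject meets the 50% threshold on one baseline and not on the other. Table 1 adds a further conflict: it explains SALT50 (without subscript) as an absolute change and keeps the subscripted form for relative regrowth, while Sections 2.2.2 and 9.4 use the unsubscripted term for a relative improvement.

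**The case against.** The strongest reply is that the plan already contains the remedy. Absolute change in SALT and ALODEX is a secondary endpoint on both baselines, medians accompany the means, maintenance has its own durability endpoint, and no inferential analysis is planned. On this view only a line on zero denominators is missing, which a SAP often supplies. Section 9.4.2 defers other parameters to a SAP, and no separate SAP text that settles the point is included in the combined document. Most of this stands and keeps the point small. It does not remove it: the endpoint is defined as a mean, and a median cannot restore values that do not exist.

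It is also fair to say that the illustrations are constructed. The −16.5% needs a subject going from exactly 1 to 30, and the −300% bound needs full relapse to the parent baseline.

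Four stronger readings are tempting and are not supported:

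- *The primary result is compromised.* It divides by the parent baseline, which is at least 30. The durability endpoint, absolute changes and parent-baseline responder rates are also untouched.
- *The method of averaging is wide open.* The wording of Section 9.4.1 taken alone could mean mean change over mean baseline, but the Section 9.4 formula and the planned median and SD largely settle the per-subject reading.
- *ALODEX has the same proven defect.* Its scale is not given, so a score of 0 is an inference. A zero at the parent baseline is implausible, since entry there required at least 30% scalp hair loss.
- *The mean will be badly distorted.* Without a Visit 1 distribution, nobody can say how often low scores occur.

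**Conclusion.** The point holds as a minor one. As written, the Visit 1-based percent change in SALT has no value for a subject entering at 0. It scores a relapsing SALT75 responder at −300% or worse against a maximum of +100%. The same applies to ALODEX only if its scale reaches 0. The −300% bound assumes that the Visit 9 score is carried over and that the subject returns to the parent baseline; a repeated Visit 1 score after delayed entry may be higher. The size of any effect on the reported means is unknown. The harm is confined to secondary descriptive tables, shown pooled and by prior treatment, but it falls on the subjects whom the maintenance objective concerns.

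**What to change.** 1. For the topical period, use the planned absolute change from Visit 1 in SALT and ALODEX as the summary, in place of the mean percent change with a Visit 1 denominator.
2. If the percent table is kept as supportive, lead with the median, and report how many subjects had a Visit 1 score of 0 together with their follow-up scores.
3. If a percent scale is wanted for SALT, (Visit 1 − visit)/ATI-501-AUAT-201 baseline is an option, with a denominator of at least 30. State that it can exceed +100% when Visit 1 is worse than the parent baseline. Do not assume that floor for ALODEX.
4. State in Section 9.4.1 that percent change is computed per subject and then averaged, in line with Section 9.4.
5. In Section 2.2.2 and the synopsis endpoint list, tie SALT50 and SALT75 to the ATI-501-AUAT-201 baseline, as Section 9.4 does. Label any ≥50% or ≥75% rate from Visit 1 as further regrowth during topical treatment. Reconcile the Table 1 entry for SALT50.

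The cost is protocol and SAP wording, with no new data or visits. The mean percent change relative to each subject's own Visit 1 score is lost or demoted.
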